6.4.3. Guidelines for the Management of Hepatotoxicity

Hepatic function abnormality is defined as any increase in ALT or AST to greater than $3 \times$ ULN and concurrent increase in total bilirubin to be greater than $2 \times$ ULN. Concurrent findings are those that derive from a single blood draw or from separate blood draws taken within 8 days of each other. Follow-up investigations and inquiries will be initiated promptly by the investigational site to determine whether the findings are reproducible and/or whether there is objective evidence that clearly supports causation by a disease (e.g., cholelithiasis and bile duct obstruction with distended gallbladder) or an agent other than the IP.

[figure not shown]
Cases where a subject shows an AST **or** ALT $\geq 3 \times$ ULN **and** total bilirubin $\geq 2 \times$ ULN may need to be reported as SAEs. These cases should be reported as SAEs if, after evaluation they meet the criteria for a Hy's Law case or if any of the individual liver test parameters fulfill any of the SAE criteria. IP should be **permanently discontinued** if they have an AE that meets the Hy's Law criteria (Figure 2). Similarly, a subject must be discontinued from IP, if they have any liver function test that is Grade 4 or higher and does not resolve to <Grade 4 within 72 hours. Refer to Section 7.2 for handling IP discontinuation.

6.4.3.1. Potential Drug-Induced Liver Injury (DILI) / Hy's Law

Wherever possible, timely confirmation of initial liver-related laboratory abnormalities should occur prior to the reporting of a potential DILI event. All occurrences of potential DILIs, meeting the defined criteria, must be reported as SAEs (see Appendix 3 Section 10.3 for reporting details). The criteria for identifying p-DILI events depend on whether the subject's baseline liver biochemistry is normal or abnormal (see Figure 2). If the subject experience a

change in liver function tests that meet the Hy's Law criteria, they must be discontinued from the study.

Figure 2 **Algorithm for p-DILI identification and mandatory SAE reporting in subjects with - (i) normal baseline liver biochemistry, and (ii) abnormal baseline liver biochemistry.**

The key responsibilities for investigators during p-DILI assessment include: (i) Early detection, medical evaluation (including the exclusion of other potential causes) and rapid laboratory confirmation of liver-related abnormalities, and (ii) Sponsor notification of p-DILI cases via SAE forms. Following the gathering and assessment of relevant clinical information the Sponsor is responsible for: (iii) Timely evaluation and triaging of p-DILI cases, (iv) Expedited reporting of p-DILI cases and (v) Expanded review of p-DILI cases including a detailed assessment of all available clinical information, investigations and biochemical data.

Investigators are expected to monitor ongoing routine and ad hoc hepatic laboratory test results to rapidly determine whether a subject meets p-DILI criteria. They are expected to promptly notify the Sponsor/Medical Monitor of all p-DILI cases. p-DILI cases may be identified by abnormal liver biochemistry values, whether or not they are accompanied by liver-related signs and/or symptoms. In both cases, expedited confirmation with repeat laboratory testing should occur within 3 business days using a Hepatic Laboratory Panel (ALT, AST, TB, AP). Any subject with an abnormal Hepatic Laboratory Panel that meets p-DILI criteria (see Figure 2) is a candidate for IP discontinuation. Any confirmed p-DILI events must be reported (along with a description of the clinical findings) to Sponsor as an SAE within 24 hours of confirmation.

An extensive clinical history, examination and appropriate investigations should be obtained to exclude cholestatic and other apparent causes that may explain the observed abnormalities in liver function and/or hepatic signs and symptoms. Other apparent causes include, non-exhaustively and by way of example only: infectious diseases (such as active hepatitis -A, -B and -C), congenital diseases (such as Gilbert's syndrome), neoplastic diseases (such as hepatocellular carcinoma), autoimmune diseases (such as primary biliary cirrhosis) and the use of concomitant hepatotoxic medications (such as antibiotics, the oral contraceptive pill and herbal medicines). All investigations to exclude potential causes of liver function abnormalities or hepatic signs and/or symptoms should be guided by relevant factors such as the subject's age, gender, clinical history, and signs and symptoms.

6.4.4. Guidelines for the Management of Colitis

For management of colitis see [Table 4](#).

Table 4 Colitis Management

Grade	Dose Modification	Management
Any Grade		
 Subjects should be thoroughly evaluated to rule out any alternative etiology (e.g., disease progression, other medications, infections including testing for Clostridium difficile toxin, etc.) Steroids should be considered in the absence of clear alternative etiology, even for low grade events, in order to prevent potential progression to higher grade event 
Use analgesics carefully; they can mask symptoms of perforation and peritonitis

Grade 1	No dose modification	Actively monitor frequency, consistency and appearance of stools (especially for presence of mucus or blood) and for the emergence of abdominal pain or cramps
Grade 2	If on AL101 6 mg QW: For first episode, change dose regimen to 6 mg 2 weeks on / 1 week off Second episode, decrease dose to 4 mg QW and for third episode decrease dose to 2.4 mg QW If on AL101 4 mg QW: Decrease dose to 2.4 mg QW	
 Promptly start prednisone 1 to 2 mg/kg/day or IV equivalent Evaluate for C. difficile and, if positive, treat with appropriate antibiotics If event is not responsive within 3-5 days or worsens despite prednisone at 1-2 mg/kg/day or IV equivalent, GI consult should be obtained for consideration of further workup such as imaging and/or colonoscopy to confirm colitis and rule out perforation Consult Ayala Medical Monitor if no resolution to \leq Grade 1 in 3-4 days in order to determine whether to continue to hold the dose or to discontinue IP. This will depend on the overall clinical situation. Therapy may only be restarted with the dose reduction upon resolution to \leq Grade 1 
Once improving, gradually taper steroids over \geq28 days and consider prophylactic antibiotics, antifungals and anti PCP

Grade	Dose Modification	Management
		treatment (please refer to current NCCN guidelines for treatment of cancer-related infections [Category 2B recommendation])
Grade 3-4	Permanently discontinue IP	
 Promptly initiate empiric IV methylprednisolone 2 to 4 mg/kg/day or equivalent Monitor stool frequency and volume and maintain hydration Urgent GI consult and imaging and/or colonoscopy as appropriate Ensure GI consult to rule out bowel perforation Once improving, gradually taper steroids over ≥ 28 days or as appropriate and consider prophylactic antibiotics, antifungals and anti PCP treatment (please refer to current National Comprehensive Cancer Network [NCCN] guidelines for treatment of cancer-related infections [Category 2B recommendation])

6.5. Treatment of Overdose

Any overdose of IP should be recorded in the eCRF (including quantity of the excess dose and the duration of the overdose). AEs associated with an overdose or incorrect administration of IP should be recorded in the AE eCRF. An overdose will not be considered an SAE unless the outcome of the overdose meets seriousness criteria.

For this study, any dose of IP greater than the weekly dose will be considered an overdose.

In the event of an overdose, the investigator should:

1. Contact the Sponsor's Medical Monitor immediately.
2. Closely monitor the subject for any AE/SAE and laboratory abnormalities until IP for at least 7 days.
3. Document the quantity of the excess dose as well as the duration of the overdose in the eCRF.

Decisions regarding dose interruptions or modifications will be made by the investigator in consultation with the Medical Monitor based on the clinical evaluation of the subject.

6.6. Concomitant Therapy

Concomitant medication is defined as any prescription or over-the-counter preparation, including vitamins and supplements. Use of concomitant medication from 28 days before Day 1 of Cycle 1 through 30 days after the last dose of IP must be recorded onto the eCRF from the subject's medical file. This will include trade name or generic name, strength, unit, route of administration, dosage form, frequency, indication, start and stop date(s) of administration.

6.6.1. Premedication to Prevent Hypersensitivity Reaction

Histamine is a major mediator of anaphylactic/anaphylactoid responses in man, such as those induced by Cremophor EL, an excipient in AL101. The premedication regimen below is based on clinical experience with other compounds containing Cremophor EL.

In order to prevent a hypersensitivity reaction, all subjects initiating AL101 treatment will be premedicated approximately 1 hour prior to the infusion of AL101 with the following regimen:

- H1-blocker (for example, diphenhydramine 25 to 50 mg oral or equivalent), and
- H2-blocker (for example, famotidine 20 to 40 mg oral or equivalent).

For subjects who remain on study for more than 4 doses of AL101 without any evidence of infusion-related reaction, modification of the premedication regimen may be considered at the discretion of the investigator, with notification of the Sponsor's Medical Monitor. At this time, 1 of the 2 histamine blockers may be discontinued; if there is still no evidence of infusion-related reaction with the next 2 doses of AL101, the other may be discontinued. If under this discontinuation plan, the subject has an infusion-related reaction resulting in medical treatment, premedication with H1- and/or H2-blockers (as appropriate) should be resumed for subsequent doses.

If a subject experiences a Grade 3 or 4 infusion-related reaction despite pretreatment with the H1- and H2-blockers then the subject, if re-treated, should also be premedicated with corticosteroids (as described in Section 6.6.2) in addition to the H1- and H2-blockers). In the event that a subject has a repeat Grade 3 or 4 infusion-related reaction despite premedication with H1- and H2-blockers and steroid, the subject must not receive any further treatment with AL101, unless agreed by the Sponsor/Medical Monitor and investigator that it is in the subject's best interest to continue treatment (e.g. subject has had a response to therapy) and appropriate safety measures can be implemented. Such measures may include dose reduction, increased infusion time, initial lower infusion rate with gradual increases, and/or premedication with multiple doses of dexamethasone. These measures have been used to allow re-treatment after infusion reactions with other agents, including IXEMPRA and Taxol (Peereboom, 1993).

6.6.2. Premedication with Corticosteroids

All subjects will receive premedication with corticosteroids as prophylaxis utilizing the approximately following regimen.

- 8 mg dexamethasone Per Os (PO) the night before each infusion
- 8 mg dexamethasone PO or IV within 30 minutes prior to dosing
- 8 mg PO every 8 hours for an additional 4 doses starting about 4 to 8 hours after the infusion is finished
- Repeat for the first 4 doses (first cycle).

If there are no GI toxicities following the first 4 infusions, the number of additional doses following the future infusions can be decreased from 4 to 2 doses of 8 mg PO every 8 hours.

Further tapering should only be considered if, in the opinion of the investigator, steroid side effects are an issue and after discussion with the Sponsor's Medical Monitor.

Other steroids, such as budesonide or prednisone may be used utilizing "prednisone equivalent" conversions.

6.6.3. Allowed Medications

All treatments that the investigator considers necessary for a subject's welfare may be administered at the discretion of the investigator in keeping with the community standards of medical care. All concomitant medication will be recorded on the eCRF including all prescription, over-the-counter (OTC), herbal supplements, and IV medications and fluids. If changes occur during the study period, documentation of drug dosage, frequency, route, and date may also be included on the eCRF.

All concomitant medications received within 28 days before the first dose of IP and 30 days after the last dose of IP should be recorded. Concomitant medications administered after 30 days after the last dose of IP should be recorded for SAEs and AESIs. In addition, all prior therapies for BC should be recorded as specified in Section 8.2.1.

Allowed concomitant therapies:

- Glucocorticoids (for instructions on premedication with corticosteroids refer to Section 6.6.2).
- In case of toxicity (e.g., GI AEs), per discretion of the investigator and in consultation with the Sponsor's Medical Monitor, dexamethasone (for example 4-8 mg every 6 hours for up to 72 hours, starting 12 hours before AL101 administration or per institution guidelines) will be permitted.
- Palliative radiation therapy to a limited field (e.g., painful bone metastasis, painful lumps), *if it is not the sole site of measurable and/or assessable disease*, is allowed any time during study participation with prior approval of the Sponsor's Medical Monitor.

6.6.4. Prohibited Concomitant Medication

Medications specifically prohibited in the exclusion criteria are not allowed during the ongoing study. If there is a clinical indication for any medication or vaccination specifically prohibited during the study, discontinuation from study therapy or vaccination may be required. The investigator should discuss any questions regarding this with the Sponsor's Medical Monitor. The final decision on any supportive therapy or vaccination rests with the investigator and/or the subject's primary care physician. However, the decision to continue the subject on study therapy or vaccination schedule requires the mutual agreement of the investigator, the Sponsor and the subject.

Subjects are prohibited from receiving the following therapies during the Screening and Treatment periods (including retreatment for post-complete response relapse) of this study:

- Prior treatment with gamma secretase inhibitors.
- Exposure to any investigational drug within 4 weeks or 5 half-lives whichever is longer or concurrently with IP administration.
- Chronic systemic glucocorticoid use (high dose defined as > 10 mg/day prednisone or equivalent).
- Use of any herbal supplements within 1 week prior to IP administration.
- Use of medications causing Torsades de Pointes within 1 week or 5 half-lives (whichever is

longer).

- Use of strong inhibitors of CYP3A4 within 1 week or 5 half-lives (whichever is longer) or strong inducers of CYP3A4 within 2 weeks or 5 half-lives (whichever is longer). Refer to Section 10.5.

Subjects who, in the assessment by the investigator, require the use of any of the aforementioned treatments for clinical management should be removed from the study. Subjects may receive other medications that the investigator deems to be medically necessary.

The Exclusion Criteria describes other medications that are prohibited in this study.

There are no prohibited therapies during the post-treatment follow-up period.

6.7. Intervention after the End of the Study

No formal open-label extension is planned.

7. DISCONTINUATION OF INVESTIGATIONAL PRODUCT AND/OR STUDY

7.1. Stopping Rules

The Simon two-stage optimal design includes pre-specified stopping rules (see [Figure 1](#)).

7.2. Discontinuation of Investigational Product

In some instances, it may be necessary for a subject to permanently discontinue IP.

Dosing of IP must be interrupted for any serious adverse reactions assessed by the investigator as related to IP. Restart of dosing may be considered upon approval by the Sponsor's Medical Monitor (or designee) after resolution of IP treatment-related events to baseline.

Discontinuation of IP does not represent withdrawal from the study. Subjects may withdraw or be withdrawn from IP at any time.

A subject may discontinue IP for reasons including but not limited to:

- Adverse event
- Death
- Lost to follow-up
- Non-compliance with study drug
- Physician decision
- Pregnancy
- Progressive disease
- Protocol deviation
- Study terminated by Sponsor
- Withdrawal by subject

The reason for subject discontinuation from IP will be recorded in the eCRF.

Please refer to [Section 6.4](#) for AL101 dose modifications and toxicity management which may lead to IP discontinuation. Pregnancy is a mandatory criterion for permanent discontinuation of IP. Any subject being managed with dose interruption for toxicity should have their study assessments followed per SoA.

All subjects who permanently discontinued IP will undergo an End of Study visit. For subjects who have discontinued IP due to reasons other than disease progression, tumor assessment will be continued at the protocol-specified schedule until documented disease progression or initiation of subsequent anticancer therapy, whichever comes first. See SoA ([Section 1.3](#)) for data to be collected at the End of Study visit.

7.3. Withdrawal from the Study

Subjects have the right to withdraw from the study at any time and for any reason without prejudice to their future medical care by the investigator or at the institution.

A subject may withdraw from the study for reasons including but not limited to:

- Death
- Withdrawal by subject
- Lost to follow-up
- Study terminated by Sponsor

The subject will be permanently discontinued both from the IP and from the study at that time.

If the subject withdraws consent for disclosure of future information, the Sponsor may retain and continue to use any data collected before such a withdrawal of consent.

If the subject withdraws from the study, he/she may request destruction of any samples taken and not tested, and the investigator must document this in the site study records.

If a subject is withdrawn from the study, every effort should be made to determine the reason. This information will be recorded on the subject's eCRF. Subjects who withdraw from the study, regardless of cause, should undergo all EOS assessments as specified in Schedule of Activities (SoA; Section 1.3). Follow-up visits will be scheduled, per protocol.

The Sponsor reserves the right to terminate the study at any time for any reason. Such reasons may be any of, but not limited to, the following:

- Lack of efficacy of the IP;
- Occurrence of AEs unknown to date in respect of their nature, severity, and duration or the unexpected incidence of known AEs;
- Medical, scientific, ethical, or administrative reasons affecting the continued performance of the study.

Regulatory Authorities also have the right to terminate the study for any reason.

7.4. Lost to Follow-up

A subject will be considered lost to follow-up if he or she repeatedly fails to return for scheduled visits and is unable to be contacted by the study site.

The following actions must be taken if a subject fails to return to the clinic for a required study visit:

- The site must attempt to contact the subject and reschedule the missed visit as soon as possible and counsel the subject on the importance of maintaining the assigned visit schedule and ascertain whether or not the subject wishes to and/or should continue in the study.

- Before a subject is deemed lost to follow up, the investigator or designee must make every effort to regain contact with the subject (where possible, 3 telephone calls and, if necessary, a certified letter to the subject's last known mailing address or local equivalent methods). These contact attempts should be documented in the subject's medical record.
- Should the subject continue to be unreachable, he/she will be considered to have withdrawn from the study.

Discontinuation of specific sites or of the study as a whole are handled as part of Appendix 1 (Section 10.1).

8. STUDY ASSESSMENTS AND PROCEDURES

- Study procedures and their timing are summarized in the SoA. Protocol waivers or exemptions are not allowed.
- Immediate safety concerns should be discussed with the Sponsor immediately upon occurrence or awareness to determine if the subject should continue or discontinue IP.
- Adherence to the study design requirements, including those specified in the SoA, is essential and required for study conduct.
- All screening evaluations must be completed and reviewed to confirm that potential subjects meet all eligibility criteria. The investigator will maintain a screening log to record details of all subjects screened and to confirm eligibility or record reasons for screening failure, as applicable.
- Procedures conducted as part of the subject's routine clinical management (e.g., blood count) and obtained before signing of the ICF may be utilized for screening or baseline purposes provided the procedures met the protocol-specified criteria and were performed within the time frame defined in the SoA.

8.1. Efficacy Assessments

Planned time points for efficacy assessments are provided in the SoA (Section 1.3).

8.1.1. Response Evaluation Criteria in Solid Tumors (RECIST) v1.1

The primary efficacy endpoint, ORR, will be evaluated using RECIST v1.1 ([Eisenhauer, 2009](#)) as described in Section 10.6 (Appendix 6). A repeat of tumor imaging will be required for the purposes of confirmation of response (i.e., partial response, and/or complete response). The confirmation scan should be no earlier than 4 weeks following the first indication of response.

In addition to local imaging assessments performed by the investigator, scans will be collected and held for possible future retrospective independent evaluation. The investigator is responsible for diagnostic and treatment decisions concerning their subjects.

Disease staging will be collected at diagnosis and Screening for this protocol, prior to any treatment initiation. The minimum duration of stable disease will be defined as ≥ 4 weeks in determining the best overall response. To document evidence of prior disease progression, tumor measures prior to baseline assessments may be requested by the Sponsor.

The imaging requirements are provided in [Table 5](#).

Table 5 Imaging Guidelines

Study Period	Schedule	Imaging (RECIST 1.1)
Screening	Within 28 days prior to day 1	
At screening, the following imaging scans are required:
 
 1. Brain MRI (preferred) or CT (acceptable) with contrast 2. CT of chest 3. CT of abdomen 4. CT of pelvis 5. Bone scan
Treatment	Every 8 weeks (\pm 3 days) until disease progression	
Follow-up scans at 8-week intervals, the following image scans are required:
 
 1. Brain MRI/CT with contrast for known or suspected disease, can be done every 12 weeks; same modality as screening should be used throughout the study. 2. CT of chest 3. CT of abdomen 4. CT of pelvis 5. Bone scan to be done every 16 weeks, if bone metastases at Screening
End of Study(EOS) Visit	30 days post last IP (\pm 7 days)	
At EOS, the following image scans are required:
 
 1. Brain MRI/CT with contrast for known or suspected disease; same modality throughout the study. 2. CT of chest 3. CT of abdomen 4. CT of pelvis 5. Bone scan, if indicated for known or suspected disease
Long-Term Follow-up	Every 3 months (\pm 7 days) until disease progression or until the subject initiates another anti-cancer therapy	
Only in subjects who discontinued IP due to toxicity, the following Long-Term Follow-up image scans are required:
 
 1. Brain MRI/CT with contrast for known or suspected disease; same modality throughout the study. 2. CT of chest 3. CT of abdomen 4. CT of pelvis 5. Bone scan, if indicated for known or suspected disease
Confirmation of Response Scan	The confirmation scan should be no earlier than 4 weeks following first indication of response (PR or CR)	
For confirmation no earlier than 4 weeks following a PR or CR, the following are required:
 
 1. Brain MRI/CT with contrast for known or suspected disease; same modality throughout the study. 2. CT of chest 3. CT of abdomen 4. CT of pelvis 5. Bone scan, if indicated for known or suspected disease

8.1.2. Patient Reported Outcome: European Organization for Research and Treatment of Cancer Quality of Life Questionnaire 30 questions (EORTC QLQ-C30) and Breast Cancer 45 Questions (EORTC QLQ-BR45)

The EORTC QLQ-C30 and EORTC breast cancer module QLQ-BR45 will be administered during the study every 4 weeks before IP administration.

EORTC QLQ-C30 was developed as an instrument to measure cancer subjects' physical, psychological and social functions (Kaasa, 1995). The questionnaire is composed of 5 multi-item scales (physical, role, social, emotional and cognitive functioning) and 9 single items (pain, fatigue, financial impact, appetite loss, nausea/vomiting, diarrhea, constipation, sleep disturbance and quality of life) (Kyriaki, 2001). It is validated and reliable and has been used successfully in various types of cancer, including BC (Mierzynska, 2020).

EORTC QLQ-BR23 was developed as an add-on instrument to EORTC QLQ-C30, to measure specifically measure breast cancer quality of life using 23 items. Recently, it was updated to include 45 items (EORTC QLQ-BR45) to include 23 items from the QLQ-BR23 and 22 new items (Bjelic-Radisic, 2018). The new items contain two multi-item scales: a target symptom scale and a satisfaction scale. The target symptom scale can be divided into three subscales: endocrine therapy, endocrine sexual and skin/mucosa scale (Bjelic-Radisic, 2020). The new EORTC QLQ-BR45 module that provides a more accurate and comprehensive assessment of the impact of new and scalable treatments on patients' QoL.

An example of the English version of the EORTC QLQ-C30 can be found at this link:

<https://www.eortc.org/app/uploads/sites/2/2018/08/Specimen-QLQ-C30-English.pdf>

An example of the English version of the EORTC QLQ-BR45 can be found at this link:

<https://www.eortc.org/app/uploads/sites/2/2018/08/Specimen-BR45-English.pdf>

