Blood for PK ^p			X	X	X		X (predose)				X (predose, odd cycles) & Cycle 4 (with biopsy)					
Overall survival																📞 / visit ^o
EORTC QLQ-C30 and EORTC QLQ-BR45 (before infusion)		X	X				X				X				X	

Abbreviations: CBC = Complete blood count; CT = computed tomography; ECOG = Eastern Cooperative Oncology Group; EOS = end of study, EORTC QLQ-C30 = European Organization for Research and Treatment of Cancer Quality of Life Questionnaire 30 questions; EORTC QLQ-BR45 = European Organization for Research and Treatment of Cancer Quality of Life Breast Cancer Module Questionnaire 45; questions; HbA1c = glycosylated hemoglobin; HIV = human immunodeficiency virus; IHC = immunohistochemistry; MRI = magnetic resonance imaging; NICD = Notch intracellular domain; NGS = Next generation sequencing; PE = physical examination; RECIST = Response Evaluation Criteria in Solid Tumors; TSH = thyroid stimulating hormone.

Notes to Schedule of Activities:

All assessments to be performed pre-infusion unless stated otherwise.

Visit window will be ± 2 days during treatment period, except for imaging ± 3 days (if AL101 dosing is delayed by up to 7 days, then imaging can be similarly delayed); EOS and Long-term follow-up will be ± 7 days.

- a. Pre-screening assessments may be done while potential candidates are on other therapy provided that a separate pre-screening informed consent form is signed.
- b. For determining eligibility, potential candidates will undergo a pre-screening assessment to determine Notch mutation status, after signing the prescreening ICF. Available genotyping results from within the last 2 years from a commercially available or laboratory developed test (LDT) NGS assay are acceptable. If acceptable genotyping results are not available, NGS testing will need to be conducted during pre-screening using a commercially available NGS assay, LTD or other validated investigational use only (IUO) clinical trial assay using tumor biopsy from within the last 2 years. When available, NGS test results will be shared with investigators and determination of Notch mutation status and eligibility will be communicated.

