If acceptable genotyping results are not available, testing of a sample collected from a locally advanced or metastatic lesion must be conducted during pre-screening using a commercially available NGS assay, LDT or other validated investigational use only (IUO) clinical trial assay capable of detecting genetic alterations in the *NOTCH 1/2/3/4* genes. For this purpose, tumor biopsy from within the last 2 years or fresh biopsy will be needed.

After signing an informed consent, all subjects will then undergo screening assessments to determine study eligibility over a 28-day Screening period. Eligibility criteria for study entry will be assessed locally by the investigator; radiographic scans at screening and from the prior 12 months will be collected and held for possible future retrospective independent evaluation. Tumor tissue will need to be provided during the Screening period for confirmatory study-specific testing.

Starting on Cycle 1, Day 1, eligible subjects will be treated with IP intravenously (IV) QW, on Days 1, 8, 15 and 22 of each 28-day cycle. Treatment will continue until the occurrence of unequivocal radiographic disease progression per RECIST v1.1 as assessed by the investigator, or clear clinical progression as assessed by the investigator, or unacceptable toxicity, or other reasons for discontinuation.

All subjects will receive premedication with H1- and H2-blockers per institution guideline (refer to Section 6.6.1) and steroids as prophylaxis (refer to Section 6.6.2). Toxicity post-AL101 administration will be managed as specified in Section 6.4.

During the Treatment period, subjects will undergo radiographic assessments every 8 weeks (± 3 days) for review by the investigator. Radiographic scans will also be collected and held for possible future retrospective independent evaluation. Other assessments will be done as specified in the Schedule of Activities (Table 1). A repeat of tumor imaging will be required for the purposes of confirmation of response (i.e., partial response, and/or complete response). The confirmation scan should be no earlier than 4 weeks following the first indication of response.

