9.3.3. Efficacy

9.3.3.1. Definitions of Efficacy Endpoints

Primary: ORR, defined as the proportion of subjects who have a best overall response (BOR) of CR or PR as determined using RECIST v1.1. BOR is defined as the best response recorded between the date of first dose of IP and the date of subsequent anti-cancer therapy. A BOR of CR or PR requires confirmation of the assessment no earlier than 4 weeks later.

Other efficacy endpoints are as follows:

- Progression free is defined as the interval from the start of study treatment to the earlier of the first documentation of disease progression or death from any cause.
- Clinical Benefit Response is defined as SD+PR+CR.
- DOR, defined as the interval from the first documentation of CR or PR to the earlier of the first documentation of disease progression (per RECIST v1.1) or death from any cause.
- OS, defined as the time from the date of start of treatment to the date of death from any cause. Subjects who are lost to follow-up and those not known to have died by the cut-off date for analysis will be censored on the date the subject was last known alive, or the data cut-off date, whichever is earlier.

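### The 4-week minimum for stable disease is shorter than the time to the first scheduled on-treatment scan, so it excludes almost no one and lets early off-schedule scans count as clinical benefit

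*Combined protocol and SAP*

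**What the plan says.** Section 8.1.1 states: "The minimum duration of stable disease will be defined as" at least 4 weeks when best overall response is determined. It does not say from which date that duration is counted.

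Section 9.3.3.1 states: "Clinical Benefit Response is defined as SD+PR+CR". It adds no duration threshold. It requires confirmation for CR and PR only, and takes best overall response as the best reading between first dose and the next anti-cancer therapy.

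On timing, Section 4.1 says that "subjects will undergo radiographic assessments every 8 weeks (± 3 days) for review by the investigator". Table 5 in Section 8.1.1 agrees ("Follow-up scans at 8-week intervals"). The notes to the Schedule of Activities add that "if AL101 dosing is delayed by up to 7 days, then imaging can be similarly delayed". Table 5 also requires an EOS scan "30 days post last IP", with a window of 7 days either side. Section 8.6 allows any on-treatment procedure to be done at an unscheduled visit, including to evaluate disease status.

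Section 3 lists the proportion with PFS at 6 months as a separate secondary endpoint.

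**The concern.** A minimum duration for stable disease should keep a very early scan, taken before the disease has had time to progress, from being counted as disease control. Here the minimum is half the scan interval, so it does no work at scheduled on-treatment scans. It matters only for scans outside that schedule, and there it is permissive. A subject with stable disease on an unscheduled week-5 scan and progression at week 8 has a best overall response of stable disease and counts as clinical benefit. A subject with the same disease course, scanned only at week 8, is a progressor.

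The study is open-label and investigator-assessed. What is at stake is the meaning and comparability of the first-listed secondary efficacy endpoint.

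**Working it through.** The documents give no rate, power or sample size for clinical benefit, so there is no stated figure to reproduce. The check is date arithmetic, in days elapsed since Cycle 1 Day 1.

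**Scheduled on-treatment scans** (Sections 4.1 and 8.1.1)
- Minimum for stable disease: 4 × 7 = 28 days.
- Earliest first scan: 56 − 3 = day 53. Latest: 56 + 3 = day 59, or 59 + 7 = day 66 with the permitted dosing delay.
- Margin: 53 − 28 = 25 days. No scheduled on-treatment scan can fail the rule.

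**EOS scans in early stoppers** (30 ± 7 days after last dose, so 23 to 37 days after it)
- Day 1 dose only (0 days elapsed): days 23 to 37. The rule excludes stable disease on days 23 to 27 only.
- Last dose Day 8 (7 elapsed): 7 + 23 = 30 to 7 + 37 = 44. Nothing is excluded.
- Last dose Day 15 (14 elapsed): days 37 to 51. Nothing is excluded, and the whole window precedes day 53.
- Last dose Day 22 (21 elapsed): days 44 to 58. Nothing is excluded, and part of the window precedes day 53.

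The day 23 to 27 exception assumes counting from first dose. If duration is counted from the screening scan, which may be up to 28 days earlier, even that exception may disappear.

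**Unscheduled scans** (Section 8.6). Stable disease from day 28 onward meets the rule. Because Section 9.3.3.1 keeps the best reading, later progression at week 8 does not remove it.

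**Scale, for illustration only.** Assume exponential PFS, S(t) = 0.5^(t/median), with 8 weeks = 1.84 months and 24 weeks = 5.52 months.
- Median 5.4 months (Section 2.2, first-line single-agent chemotherapy): 0.5^(1.84/5.4) = 79% progression-free at 8 weeks; 0.5^(5.52/5.4) = 49% at 24 weeks.
- Assumed median 2 months: 53% and 15%. Assumed median 3 months: 65% and 28%.

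These figures show how far non-progression at the first scan can differ from non-progression at 24 weeks. The 2- and 3-month medians are not from the documents.

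**The case against.** The strongest reply is that little depends on this endpoint. Section 9.3 limits significance testing to the Simon two-stage analysis, so clinical benefit has no hypothesis, threshold or stopping role, and being listed first is not a testing hierarchy. Durable control is already measured by PFS at 6 months, with PFS and duration of response beside it. The protocol says openly that clinical benefit means CR, PR or stable disease, and Section 9.3 leaves technical detail to an SAP to be finalized before database lock. All of this stands, and it keeps the point small.

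Several stronger readings are tempting and are not supported:
- A reader might infer that the minimum never acts on any scheduled scan. The EOS scan of a single-dose subject on days 23 to 27 is an exception.
- A reader might infer that a clinical benefit rate of 50 to 80% is to be expected from an inactive drug. The 5.4-month median comes from patients on first-line chemotherapy and the shorter medians are assumptions, so neither describes patients without effective treatment.
- A reader might infer that clinical benefit must be redefined at 24 weeks. Nothing in the documents sets that threshold, and it would largely duplicate 6-month PFS.
- A reader might infer that early unscheduled scans are common or sought. The documents allow them but give no sign of their frequency.

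It is also fair to say that a 53-day minimum still excludes no one scanned on schedule. It adds no durability; its purpose is to stop earlier scans from qualifying.

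**Conclusion.** The point holds as a minor definitional defect. The 28-day minimum is at least 25 days shorter than the time to the first scheduled on-treatment scan and excludes no one there. Off that schedule, it admits stable disease seen at weeks 4 to 7 whatever week 8 shows. The clinical benefit rate is in effect the proportion without progression at the first evaluable scan, and for some subjects that scan may come well before week 8.

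The timing result rests only on the protocol's own dates, counted from first dose. How many subjects are affected cannot be derived, because it depends on the number of early stoppers and unscheduled scans. The primary response-rate analysis and the Simon decision rule are untouched.

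**What to change.** 1. In Sections 8.1.1 and 9.3.3.1, require a stable-disease assessment at least 53 days after first dose (8 weeks less the 3-day window) for a best overall response of stable disease. State that duration is counted from first dose.
2. Count subjects whose only stable-disease reading is earlier as not having clinical benefit.
3. Describe the CR + PR + stable disease rate as disease control at the first scheduled assessment, noting that a subject not evaluable then but stable later also counts. Refer to PFS at 6 months for durability. Align the endpoint wording in the Synopsis and Section 3.
4. A 24-week version is optional. If reported, it should allow the scan window: 168 − 3 = at least 165 days.
5. Reconcile the imaging rules after treatment stops. Section 7.2 keeps the protocol schedule for all who stop for reasons other than progression. The Synopsis, Section 4.1 and Table 5 give 3-monthly imaging for those who stop for toxicity, and Table 5 limits it to them. Later disease status in early stoppers depends on which applies.

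Items 1 to 3 are text changes, with no extra scans and no change to sample size. The downside is a slightly lower clinical benefit rate, because some early stoppers will no longer count as stable disease. Making the change before database lock avoids a post hoc choice.
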